## List of Abbreviations:

PCa	Prostate Cancer
CH	Celebration Health
ESU	Electrosurgical Generator Unit
FDA	Food and Drug Administration
FH	Florida Hospital
IFU	Instructions for Use
PI	Principal Investigator
PLND	Pelvic Lymph Node Dissection
RARP	Robot-Assisted Radical Prostatectomy
RF	Radiofrequency
USA	United States of America

## Introduction

This document is a protocol for a human research study. This study is to be conducted according to United States standards of Good Clinical Practice in accordance with applicable Federal regulations and institutional research policies and procedures.

Prostate cancer (PCa) is the third most common cause of cancer related death in the United States and is the most prevalent non-cutaneous cancer [1]. Pelvic lymph node dissection (PLND) following robot-assisted radical prostatectomy (RARP) is an established technique for determining lymph node metastases [2]. The most frequent post-operative complication of PLND is lymphocele formation. Lymphoceles occur as a result of lymph leakage from lymphatic channels that have been cut during dissection. The Principal Investigator (PI) has previously published findings of an occurrence rate of 51% for lymphocele formation with 15.4% from them being clinically symptomatic. The overall frequency of symptomatic lymphocele in patient's that underwent bilateral PLND was equal 6.6% of the evaluated group in this publication [3].

We hypothesize that the incidence of lymphocele's should decrease significantly by attending to careful sealing of these channels using adequate hemostatic tools [3].

## Background Information and Scientific Rationale

Bovie Medical Corporation's J-Plasma® helium based plasma technology is a hemostatic tool with FDA clearance for the cutting, coagulation, and ablation of soft tissue. The J-Plasma® system consists of an electrosurgical generator unit (ESU), a handpiece, and a supply of helium gas. Radiofrequency (RF) energy is delivered to the handpiece by the ESU and used to energize an electrode. When helium gas is passed over the energized electrode, a helium plasma is generated which allows for conduction of the RF energy from the electrode to the patient in the form of a precise helium plasma beam. The energy delivered to the patient via the helium plasma beam is very precise and cooler in temperature in comparison to other surgical energy modalities such as standard RF monopolar energy. Previous studies comparing J-Plasma® to other energy sources demonstrated less or comparable lateral and depth of thermal spread for J-Plasma® in porcine peritoneum, bladder, and small intestine [4]. The precise delivery of energy and minimal thermal injury to collateral tissue makes J-Plasma® a useful surgical tool in procedures such as radical prostatectomy where minimizing damage to collateral tissue is crucial to preserving sexual function and continence. As an example, J-Plasma® has been shown to be clinically effective in the treatment of endometriosis on fallopian tubes, ovaries, and other delicate structures where current RF energy sources cannot be used due to risk of damage [5,6].

This study protocol will evaluate the efficacy of the J-Plasma® helium based plasma technology in the reduction of lymphoceles following PLND during RARP. The J-Plasma® handpiece will be used during the PLND by dissecting the lymph nodes and sealing the lymphatic channels to prevent lymph leakage.

## Study Objectives

The primary objective of this study is to evaluate the efficacy of the J-Plasma® helium based plasma technology in the reduction of lymphoceles following PLND during RARP.

### PRIMARY OBJECTIVE/AIM/GOAL/HYPOTHESIS

J-Plasma® helium based plasma technology will reduce the occurrence of lymphoceles when used to perform PLND during RARP.

### SECONDARY OBJECTIVE/AIM/GOAL/HYPOTHESIS

N/A

## Study Design

### RESEARCH DESIGN

The study will be a single institution, single arm prospective trial where by 100 patients will be enrolled.

Participants evaluated and scheduled for a PLND during Robotic Assisted Radical Prostatectomy by [name] who have met the study inclusion criteria and who have also given informed consent will be enrolled. Enrolled participants will have their PLND performed using J-Plasma® for dissection and sealing of lymphatic channels. An abdominal-pelvic ultrasound will be completed at a follow-up period ranging from 4-12 weeks post operatively to determine if a lymphocele is present as this is the standard of care within [name] clinical practice for all patients who undergo a PLND during RARP. The occurrence rate of lymphoceles in this trial group of 100 patients will be compared to retrospective data of 100 patients acquired from the IRB approved Urologic Robotic Surgery Outcomes Registry # 237998 using the same inclusion/exclusion criteria as defined for enrollment in this protocol and from other published data to determine if the occurrence rate has been reduced.

### STUDY AGENT, DEVICE, AND/OR INTERVENTION DESCRIPTION

The study will be conducted using components of the Bovie Medical J-Plasma® system that have received FDA clearance and are currently commercially available. The J-Plasma® handpieces were cleared under FDA 510k numbers K112233 and K151325 for the delivery of helium gas plasma for cutting, coagulation, and ablation of soft tissue. The Bovie Ultimate high frequency electrosurgical generator was cleared under FDA 510k number K142975 for delivery of RF energy and/or helium gas plasma to cut, coagulate, and ablate soft tissue. Therefore, the cutting, coagulation, and ablation of soft tissue during PLND would be considered on label for the study devices.

## STUDY SITE(S)/LOCATION(S) AND NUMBER OF SUBJECTS

Florida Hospital Celebration Global Robotics Institute:  
Estimated number of subjects at Florida Hospital sites: 100

Total number of all sites: 1  
Estimated number of subjects at all sites combined: 100

## MULTI-SITE RESEARCH LOGISTICS/COMMUNICATION PLAN

N/A

## RESEARCH CONDUCTED IN A FOREIGN COUNTRY

N/A

## COMMUNITY-BASED PARTICIPATORY RESEARCH

N/A

## Subject Selection

### VULNERABLE POPULATIONS (IF APPLICABLE)

N/A

Employees: If an FH employee meets inclusion criteria their non-participation will not affect their employment status.

## INCLUSION CRITERIA

Must answer yes to all:

1. Age 18 – 80
2. Primary diagnosis of Prostate Cancer (ICD-10:C61)
3. Prostate Specific Antigen (PSA) level  $\geq$  10ng/mL and/or Gleason Score  $\geq$  7
4. Planned Elective Robotic Assisted Radical Prostatectomy with planned pelvic lymph node dissection.
5. Willing and able to return to clinic for standard of care abdominal ultrasound within 12 weeks post operatively.
6. Able to provide informed consent

## EXCLUSION CRITERIA

Must answer no to all:

1. Patient is unwilling or unable to sign or understand informed consent
2. Patient resides outside of the United States
3. Performance of Lymph node dissection was aborted.
4. Presence of implanted mechanical cardiac device.

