***Adults Unable to Consent***

N/A- informed consent by the patient is a requirement for inclusion.

DOCUMENTATION OF INFORMED CONSENT PROCESS

Documentation of the informed consent process is required to establish that the subject was accurately and adequately informed and that no study-related procedures were initiated prior to obtaining informed consent. A research team member will note in the source documentation the consent process, date consent was obtained and that consent was obtained prior to initiating any research procedures.

RANDOMIZATION

N/A

STUDY VISITS

Visit 1: Inclusion and exclusion criteria will be reviewed. If the patient meets criteria, he will be invited to participate in the research study. The patient will be given the informed consent and it will be reviewed with the patient and all questions will be answered.

Visit 2: Day of Surgery. The only non-standard of care item will be with the use of The Bovie J plasma at lymph node dissection and will not be billed to patient.

Visit 3: Patient returns to [name] clinical practice for routine standard of care exam and abdominal ultrasound done at Florida Hospital Celebration.

The following table identifies the procedures in relation to the study timeline.

STUDY VISIT SCHEDULE	Visit 1 Screening/Consent	Visit 2 Surgery day	Visit 3 Abdominal US 8wks post op +/- 4 weeks	
Inclusion and Exclusion Criteria	X			
Informed Consent	X			
RARP with PLND		X		
Abdominal US			X	

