### POTENTIAL RISKS

Risks associated with robotic radical prostatectomy as discussed and stated by the physician and included in the surgery consent signed by the patient regardless of enrollment in this study include: severe loss of blood, damage to surrounding organs, tissues, vessels, infection / any of which may necessitate a return to surgery, cardiac arrest which may result from the performance of any surgery/ procedure(s), and in some cases, may lead to partial or permanent disability or death. Additional risks may include, but are not limited to: urinary incontinence, erectile dysfunction, rectal/bowel/ureter injury, bladder neck contracture, pulmonary embolism, urine leak, pneumonia, problems related to positioning and endotracheal tube, blood transfusion, embolus from pneumo-peritoneum, unrecognized injuries and lymphocele formation.

JPlasma® has minimal lateral and depth of thermal spread in a variety of tissue types however; possible risks associated with JPlasma® are: unintended surgical site burns due to direct contact with the cutting tip electrode. Inadvertent activation or movement of the cutting tip instrument outside the field of vision may result in injury to the patient or

surgical team. Electrosurgical devices may cause interference with pacemakers or other implants.

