### **Early Withdrawal of Subjects**

#### INVESTIGATOR WITHDRAWAL OF SUBJECTS

Patients that did not receive a pelvic lymph node dissection at the discretion of the surgeon during their robotic radical prostatectomy will be withdrawn from the study.

Patients that do not return for the abdominal ultrasound post operatively as ordered by the physician will be withdrawn from the study.

If a patient is withdrawn from the study they will be notified via telephone call by GRI Research Staff. After 3 failed attempts by phone a certified letter will be mailed to the patient as the final attempt of notification.

All withdrawn participants will be documented in the regulatory binder.

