#### DATA COLLECTION AND FOLLOW-UP FOR WITHDRAWN SUBJECTS

Patients who request withdrawal prior to the post-operative abdominal ultrasound will not be included in the final analysis as there would be unsuccessful collection of the data necessary to conclude the study's end point. Patients who request to withdraw after the abdominal ultrasound will have their data maintained in the research database up to the

point of withdrawal. This data will be included in subsequent analysis because keeping these patients in the analysis is essential for study validity.

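### Patients exposed to J-Plasma can be excluded or withdrawn after surgery, and no rule then continues their adverse-event follow-up or keeps them in a safety summary

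*Combined protocol and SAP*

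**What the plan says.** **Eligibility and exposure.** Exclusion 3 reads "Performance of Lymph node dissection was aborted" (Exclusion Criteria). Under Study Visits, eligibility belongs to the first visit: "Visit 1: Inclusion and exclusion criteria will be reviewed". The device is used at Visit 2: "The only non-standard of care item will be with the use of The Bovie J plasma at lymph node dissection". Visit 3, the ultrasound at 8 weeks ± 4 weeks, is the only post-operative visit in the schedule. Study Duration keeps participants in the study for 4 months after surgery.

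**Withdrawal.** Investigator Withdrawal of Subjects has two rules: "Patients that did not receive a pelvic lymph node dissection at the discretion of the surgeon during their robotic radical prostatectomy will be withdrawn", and "Patients that do not return for the abdominal ultrasound post operatively as ordered by the physician will be withdrawn from the study". The section on data and follow-up for withdrawn subjects deals only with patients who ask to leave: "Patients who request withdrawal prior to the post-operative abdominal ultrasound will not be included in the final analysis". The reason it gives is the missing ultrasound endpoint.

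**Adverse events.** Recording and Notification of Adverse Events requires questioning at each subject contact, immediate entry of all events in source and CRF, and reporting under IRB guidelines. Mitigation of Risks relies on follow-up visits to monitor side effects. The Safety Monitoring Plan has the investigator review data every 25 enrolled subjects or every 4 months. Potential Risks names "unintended surgical site burns due to direct contact with the cutting tip electrode" for the device. The only planned outcome analysis is lymphocele incidence (Primary Objective Analysis).

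**The concern.** Needing a scan is a sensible condition for the lymphocele analysis. For harms, the relevant condition is exposure to the device. The protocol has a single notion of being in or out of the study and applies it to both purposes. A patient whose dissection is started with J-Plasma and then abandoned meets an exclusion criterion after exposure. A patient who had the dissection but does not attend the scan is withdrawn from the study, not just from the endpoint.

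At stake is the completeness of the device's safety account in a single-arm study of 100 patients, funded by the manufacturer and without a DSMB. At that size, one or two patients missing from the numerator or denominator can change what the report says about harm.

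**Working it through.** **Is there a plan figure to reproduce?** No. The documents state no injury rate, abort rate, missed-scan rate, safety endpoint or safety population. The only planning number is 100 enrolled, and Sample Size Determination gives no dropout allowance. The check is therefore mainly a reading of sections side by side.

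| Situation | Exposed? | What the protocol does | Adverse-event rule afterwards |
|---|---|---|---|
| Dissection started with J-Plasma, then aborted | Yes | Meets exclusion 3 | None stated |
| No dissection, at the surgeon's discretion | Possibly not: the device is used only at the dissection | Withdrawn by the investigator | None stated |
| Dissection done, scan missed | Yes | Withdrawn by the investigator | None stated |
| Patient asks to leave before the scan | Yes, if after the dissection | Left out of the final analysis | None stated |
| Patient asks to leave after the scan | Yes | Data to that point kept and analysed | None stated |

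**Follow-up.** Adverse events are sought at subject contacts and follow-up visits. Visit 3 is the only scheduled post-operative one, so a patient who misses it loses that contact and is withdrawn for missing it. The only contact then specified is a call, or after three failed calls a letter, to notify him of the withdrawal. Four months is about 17.4 weeks (4 × 365.25 / 12 / 7). The Visit 3 window closes at 12 weeks, so at least 17.4 − 12 = 5.4 weeks of planned participation follow it with no scheduled contact for anyone. Death and hospitalisation are defined as serious during a protocol-defined surveillance period that is not tied to the 4 months, so withdrawal could be read as ending it. The general surgical risk list includes injuries not recognised at the time, so late recognition is foreseeable.

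**Reporting.** Entry in a CRF does not settle who is counted in the final report. With no safety set defined, a report restricted to scanned patients would be consistent with the text.

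**Illustration with assumed inputs.** Let q be the true device-injury rate among 100 exposed patients and w the share of injured patients whose injury is not captured or not reported. Then

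P(at least one injury seen) = 1 − (1 − q(1 − w))^100.

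| q | w = 0 | w = 0.25 | w = 0.5 | w = 1 |
|---|---|---|---|---|
| 1% | 63% | 53% | 39% | 0% |
| 2% | 87% | 78% | 63% | 0% |
| 3% | 95% | 90% | 78% | 0% |

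Example: q = 2%, w = 0.5 gives 1 − 0.99^100 = 63%.

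For the denominator, three injuries in 100 exposed is 3.0% (exact 95% CI 0.6% to 8.5%). If a report omitted exactly those three patients it would show 0/97, with an upper 97.5% bound of 1 − 0.025^(1/97) = 3.7%. That is the extreme case. The columns with w above 0 apply to late harms or to harms left out of the summary. For an intra-operative injury recorded and reported as the protocol requires, w = 0.

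**The case against.** A reader might infer that device injuries leave the safety record altogether. The documents do not support that. All adverse events must be recorded immediately and reported under IRB guidelines, with no exception for excluded or withdrawn patients, and nothing says recorded events are deleted. A burn seen during surgery precedes any withdrawal and is covered. Withdrawals are also documented in the regulatory binder.

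A reader might also infer that the investigator's safety reviews see only the reduced set. Those reviews are timed by enrolled subjects and are not limited to completers, so that is not established. Nor do the documents show that device injuries are the likeliest cause of aborted dissections or missed scans: they give no reasons or rates for either.

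Three further points stand. The rule on the final analysis concerns patients who ask to leave and the ultrasound endpoint; it is not a rule about adverse-event data. *Did not receive* a dissection may describe patients never exposed. And the notification call, if it reaches the patient, is arguably a contact at which adverse events must be asked about.

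These points narrow the concern without closing it. One call at an unspecified time is not follow-up to 4 months, the letter that replaces it when calls fail is not an enquiry about harm, and none of these rules says who is counted in the final safety summary.

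**Conclusion.** The concern holds as a gap in follow-up and reporting for exposed patients who are excluded or withdrawn by the investigator. Later-recognised harms could be missed, and affected patients could be absent from the final summary. It does not hold as a claim that injuries recognised in time go unrecorded.

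The size is unknown. Every percentage in the illustration depends on assumed q and w; it shows only that a study of 100 is sensitive to losing one or two cases. The conclusion rests on two readings of the text: that withdrawal from the study ends scheduled study contact, and that an aborted dissection can be one already begun with the device. It is worth correcting because following the withdrawal rule as written stops follow-up of exposed patients, and the correction is cheap.

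**What to change.** 1. In the two sections on investigator withdrawal and on data for withdrawn subjects, state that an aborted dissection or missed scan removes a patient from the lymphocele analysis only.
2. State in the same place that every patient in whom J-Plasma was activated stays in the safety summary, with adverse events collected to the end of the planned 4 months unless he withdraws consent for this; events up to that point are kept and reported.
3. Reword exclusion 3 as a rule for the lymphocele analysis set, applied equally to trial patients and registry controls. It should not simply be deleted, because Research Design and Primary Objective Analysis use the same criteria to select the controls.
4. Reconcile *aborted* in Exclusion Criteria with *did not receive* in the withdrawal section, so that exposed and unexposed patients are distinguished.
5. Report the numbers of aborted dissections and missed scans, with reasons.

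The cost is a protocol wording amendment and record follow-up of a few patients by the coordinator and abstractors already assigned. The reported event rate may come out less favourable.

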## Resources Available

The research team assigned to the study for screening, consenting and data collection purposes will be the Research Coordinator who is a RN and three data abstractors that work on post-operative RARP patient follow up. Two members are medical assistants with experience of screening and consenting in research as well as clinical experience in urology.

- Justify the feasibility of recruiting the required number of suitable subjects within the agreed recruitment period. [name] clinical practice sees approximately 900 patients a year in consultation for RARP as treatment for prostate cancer. Approximately 11% will be needed for enrollment.
- There is no additional surgical time needed for this study. The approximate surgical time is 90 minutes.

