***Cognitively Impaired Adults***

- During screening the health and physical is examined for inclusion and exclusion criteria including information about their past medical and social history. Information from the patient record as well as verbal questioning will be used to identify possible impairment.

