### **Study Outcome Measures (Endpoints)**

The primary outcome to be measured will be the incidence of lymphocele formation as diagnosed upon post-operative abdominal ultrasound. The incidence of lymphocele formation in patients undergoing pelvic lymphnode dissection using the JPlasma® will be compared to de-identified retrospective data of lymphocele formation without the use of JPlasma® extracted from [name] urologic outcomes registry identified by IRBnet #237998.

The following data variables and materials will be collected for analysis in this study:

- Age at day of surgery
- Pre-operative Gleason Score
- Pre-operative PSA lab value
- Clinical variables: pathology report from RARP, radiology report from abdominal ultrasound, physician notes, nurses notes.

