## Statistical Analysis Plan

### PRIMARY OBJECTIVE ANALYSIS

The primary variable of interest is the incidence of lymphocele formation measured at approximately 8 weeks post-operatively. The incidence of lymphocele formation will be compared between the 100 enrolled “treatment” group and a propensity matched “non-treatment” group that will be established using equal inclusion/exclusion criteria, this retrospective lymphocele data will be retrieved from the Urologic Robotic Surgery Outcomes Registry identified by IRBnet #237998. Additional comparisons of demographic (age, race/ethnicity) and oncological information will be accessed to ensure no differences between the two groups.

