#### MITIGATION OF RISKS

Side effects will be monitored during follow-up study visits.

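### Exclusion 4 covers only a mechanical cardiac device, so non-cardiac active implants stay eligible although the protocol names interference with other implants as a risk (minor safety wording)

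*Combined protocol and SAP*

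**What the plan says.** Exclusion Criteria, item 4, reads "Presence of implanted mechanical cardiac device". The term is not defined, and no other inclusion or exclusion criterion mentions implants.

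Under Potential Risks, the account of possible J-Plasma risks ends with "Electrosurgical devices may cause interference with pacemakers or other implants". The whole text under Mitigation of Risks is "Side effects will be monitored during follow-up study visits".

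Two places describe screening. Subject Recruitment and Screening has a researcher check the medical record, with laboratory and pathology reports singled out. The section on cognitively impaired adults adds "During screening the health and physical is examined for inclusion and exclusion criteria including information about their past medical and social history".

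The registry comparison group is to be chosen "using the same inclusion/exclusion criteria as defined for enrollment in this protocol" (Research Design). The analysis section repeats this: "established using equal inclusion/exclusion criteria".

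**The concern.** The protocol already uses exclusion to control implant risk, but applies it to only part of the risk that it names. For the remainder, the other implants, the text gives neither an exclusion nor a precaution.

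The wording is also unclear within its own scope. A pacemaker is the one implant that the risk section names, and it is an electronic device, which mechanical does not describe well. Exclusion of pacemakers was probably intended, but the criterion does not say so. The criteria are a yes/no list, and the Resources Available section assigns screening to a research coordinator and data abstractors, so the literal wording matters.

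At stake is the safety of the occasional enrolled patient who has an active implant outside the heart. Interference would arise while the device is in use, during surgery.

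**Working it through.** The check is mainly a comparison of texts. The point depends on no alpha, power or effect size.

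**1. Scope of the risk against scope of the rule**

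| | Pacemaker or defibrillator | Non-cardiac active implant | Passive implant |
|---|---|---|---|
| Potential Risks | Pacemaker named; defibrillator falls under other implants | Falls under other implants | Not distinguished |
| Exclusion 4 | Probably intended, poorly worded | Not covered | Not covered |

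**2. A test case through the criteria.** Take a man with a nerve stimulator who is otherwise suitable. The six inclusion criteria concern age, diagnosis, PSA or Gleason score, planned surgery, return for ultrasound and ability to consent. He can meet all six. The four exclusions concern consent, residence outside the United States, an aborted node dissection and an implanted mechanical cardiac device. None applies to him, so he is eligible on any reading of mechanical, because cardiac alone puts him outside Exclusion 4.

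**3. Does another section close the gap?**

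- *Screening.* Laboratory and pathology reports are unlikely to show an implant. The history review could, but no criterion would act on what it found.
- *Mitigation of Risks.* This is limited to follow-up visits. The Study Visits table has one post-operative visit, at 8 weeks plus or minus 4 weeks.
- *Recording and Notification of Adverse Events.* Specific questioning takes place at each contact. This detects events and does not prevent interference during the operation.
- *Safety Monitoring Plan.* The principal investigator reviews data for every 25 enrolled subjects or every 4 months, whichever comes first. This too comes after the event.

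None of these states a step before or during surgery.

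**4. Recruitment cost of the fix.** Resources Available gives about 900 consultations a year and says "Approximately 11% will be needed for enrollment". That figure reproduces: 100 / 900 = 11.1%. If the wider criterion caused k extra screen failures, the share needed would be (100 + k) / 900. The documents give no basis for k, so these values are illustrations and not estimates:

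- k = 2: 102 / 900 = 11.3%
- k = 5: 105 / 900 = 11.7%

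A few extra screen failures would hardly change the recruitment plan.

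**5. Comparison group.** Both design sections apply the same criteria to the registry patients, so a reworded Exclusion 4 reaches them automatically. Implant status is not a named study variable. The listed sources, "Clinical variables: pathology report from RARP, radiology report from abdominal ultrasound, physician notes, nurses notes", may contain it, but completeness is unknown.

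**The case against.** The strongest reply is that a protocol may disclose a risk without excluding everyone exposed to it. The same section lists bleeding, organ injury and burns with no matching exclusions. To exclude cardiac devices and disclose the rest is a defensible choice. The risk sentence speaks of electrosurgical devices as a class. According to Study Visits, J-Plasma at node dissection is the only item outside standard care, so routine peri-operative handling of implants presumably continues. The device labelling, which may settle the matter, is not among the documents.

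Much of this stands. There is no formal contradiction between the two sections, and routine care or labelling may already manage the risk. It does not remove the gap in the text: the protocol chose exclusion as its control for implants, stopped short of the risk that it names, and states no other control before or during surgery.

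A reader might infer more than the documents support:

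- **That J-Plasma carries more implant risk than usual electrosurgery.** The risk is worded for the class, and no comparison is given.
- **That pacemaker patients are deliberately eligible.** The wording is poor, but the likely intent is to exclude them.
- **That the number of affected patients can be stated.** No prevalence is given, and the chance of enrolling such a patient is not the chance of harm.
- **That the lymphocele comparison is biased.** The same rule applies to both groups, and nothing in the documents links implant status to lymphocele formation.
- **That the registry section needs its own amendment.** Those patients were treated without J-Plasma, so the safety reason does not reach them.

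**Conclusion.** The point holds as a minor clarification of safety wording. The conclusion that non-cardiac active implants are eligible rests on the text alone. Its practical importance cannot be sized, because the documents give neither the frequency of such implants nor the severity of interference. It also depends on what the device labelling and routine care already require, which cannot be seen here. No stated figure and no part of the primary analysis changes. The case for acting is that the change is cheap and brings one eligibility rule into line with a risk that the protocol itself states.

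**What to change.** Reword Exclusion 4 to: *Presence of a pacemaker, implantable defibrillator or other active electronic implant (cardiac or non-cardiac).* Alternatively, if the device labelling permits some active implants, name them and state the intra-operative precaution under Mitigation of Risks. Passive implants stay eligible under either route.

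The screening step should include a question about implants, since laboratory and pathology reports would not reveal one.

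The cost is one amended line, or one added sentence if the precaution route is used, together with a few extra screen failures. The drawback is that implant status may be incompletely recorded for the registry patients, so a widened exclusion might not be applied equally to both groups. No separate registry amendment is needed. If equal application is a worry, the precaution route leaves eligibility for the permitted implants unchanged in both groups.
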